Participating women also were asked to report the frequency of their vaginal dryness symptoms throughout the study. They initially reported experiencing dryness an average of 4 days out of the prior 7 days. Once participants started using VR101, the reported frequency of vaginal dryness symptoms decreased to an average of 1.3 days during the first 7 days of ring use, 0.4 days during the second 7 days of ring use and remained lower than baseline 7 days after discontinuing ring use (1.8 days out of 7 days after VR101 use had been discontinued) (all $p < 0.005$, one-tailed, normally approximated Wilcoxon signed-rank test). While 20 of 21 women reported experiencing dryness symptoms in the 7 days prior to entering the study, only 7 of 21 and 4 of 21 reported experiencing any symptoms of vaginal dryness during the first and second week of VR101 use, respectively.

J3 Bioscience, Inc.	Clinical Investigation Plan and Protocol CI02	CI02-CIP Rev. 08 Page 17 of 75
	A Pivotal Clinical Investigation to Evaluate the Safety and Efficacy of J3 Bioscience Lubricating Intravaginal Ring VR101 in Relieving Symptoms of Vaginal Dryness	

Regarding safety, no serious safety concerns or adverse events were noted or reported by the participants or clinical study staff. Participants were asked if they experienced any unusual vaginal discomfort or discharge over the course of the investigation. There were 11 reports (out of 63 total surveys) of vaginal discomfort recorded and six reports (out of 63 total surveys) of vaginal discharge. It is important to note that for both vaginal discomfort and discharge reported, all participants but one rated discomfort and discharge with the lowest intensity score possible, “minimal/minor,” and that none of the participants consistently reported unusual discomfort or discharge throughout the study. Moreover, all 21 participants that enrolled successfully completed the study, including follow-up.

In total, these results demonstrate that VR101 shows promise for safely moisturizing and lubricating the vagina and supplementing the body’s natural lubrication in peri- and post-menopausal women experiencing symptoms of vaginal dryness. A complete summary of data from the pilot investigation CI01 can be found in Clinical Investigation CI01 Final Report which is included as an attachment to the Investigator’s Brochure.

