4.2.3 Hypotheses for Claims and Usability Testing

If both the primary efficacy and safety hypotheses are met, then hypotheses for Claims 1, 2, and 3 will be tested using a hierarchical testing approach in order to control for multiplicity. Claim 1 will be tested first and if the null hypothesis is rejected, then Claim 2 will be tested. If the null hypothesis for Claim 2 is rejected, then Claim 3 will be tested. Refer to Appendix B for survey questions used to assess the validity of the following claims.

Claim 1: VR101 relieves vaginal dryness symptoms for up to 7 days in a majority of participants, as assessed by users.

Vaginal dryness severity will be assessed throughout the study using participant's ranked responses to questions in a questionnaire (see Section 5.4.5 below). Severity will be scored on a 0 to 3 scale (3 being the worst possible rating). At each visit, participants will be asked to rate their vaginal dryness over the last 24 hours and the last 7 days. **Claim 1 will be validated if the**

J3 Bioscience, Inc.	Clinical Investigation Plan and Protocol CI02	CI02-CIP Rev. 08 Page 25 of 75
	A Pivotal Clinical Investigation to Evaluate the Safety and Efficacy of J3 Bioscience Lubricating Intravaginal Ring VR101 in Relieving Symptoms of Vaginal Dryness	

p-value associated with a two-tailed Student's t-test of the mean of the paired values between the *daily* vaginal dryness severity score reported on day 7 (survey question, Visit 2) and average *weekly* vaginal dryness severity score reported over the week prior to VR101 use (survey question, Visit 1 for study group V1S2, Visit 4 for study group S1V2) is less than 0.05. If the paired differences are observed not to be normally distributed, an appropriate non-parametric test will be substituted for the two-tailed Student's t-test. Additionally, a two-tailed 95% confidence interval of the paired dryness values will be reported.

Claim 2: VR101 is easy to use by following the provided instructions for use.

Null and Alternative Hypotheses for Claim 2:

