5.4.5 Participant Assessment of Vaginal Dryness Relief (Endpoint 2 and Exploratory Endpoints)

The following 4 questions will be asked at each clinical visit as part of each Pre-Procedure Survey. These questions will also be asked during each follow-up call.

1. *Think about the last 7 days. In how many of those days did you experience any vaginal dryness? ("Vaginal Dryness Frequency")*
2. *On average, how would you rate your vaginal dryness in the last 7 days? ("Weekly-Averaged Severity of Vaginal Dryness")*

J3 Bioscience, Inc.	Clinical Investigation Plan and Protocol CI02	CI02-CIP Rev. 08 Page 43 of 75
	A Pivotal Clinical Investigation to Evaluate the Safety and Efficacy of J3 Bioscience Lubricating Intravaginal Ring VR101 in Relieving Symptoms of Vaginal Dryness	

3. *On average, how would you rate your worst day of vaginal dryness symptoms? ("Peak Severity of Vaginal Dryness")*
4. *How would you rate your vaginal dryness in the last 24 hours? ("24-hour vaginal dryness severity")*

Possible responses for question 1 are integers from 0 to 7 (assuming the ring was in place for exactly 7 days), while possible responses for questions 2-4 are as follows:

"I have not experienced vaginal dryness"	(assigned a score of 0)
"Mild"	(assigned a score of 1)
"Moderate"	(assigned a score of 2)
"Severe"	(assigned a score of 3)

Responses to Question 2 prior to ring insertion and to Question 4 following use of the first VR101 for 7 days will be used to assess the validity of Claim 1.

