8 STATISTICAL CONSIDERATIONS

8.1 Summary of Statistical Methods

The hypotheses of the clinical investigation are detailed in Section 4.2. For Primary Efficacy and Validation of Claim 1, the null hypothesis will be rejected based on a two-tailed Student's t-test ($\alpha = 0.05$) or an appropriate non-parametric two-tailed test if the data do not appear to be normally distributed.

The remainder of hypotheses will be tested using the 95% confidence interval associated with a proportion of events (e.g. SADE occurrence per number of devices used, proportion of favorable survey responses).

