8.12 Definition of Study Populations for Analysis

THE FOLLOWING STUDY POPULATIONS HAVE BEEN DEFINED FOR THIS INVESTIGATION:

Intent-to-Treat (ITT) Primary Efficacy Hypothesis Population: All patients who meet inclusion/exclusion criteria and are randomized will be included. Any missing day 0 or day 28 VHI scores will be imputed as defined in section 8.8.

J3 Bioscience, Inc.	Clinical Investigation Plan and Protocol CI02	CI02-CIP Rev. 08 Page 57 of 75
	A Pivotal Clinical Investigation to Evaluate the Safety and Efficacy of J3 Bioscience Lubricating Intravaginal Ring VR101 in Relieving Symptoms of Vaginal Dryness	

Menopausal Population: All members of the ITT population who self-report to being menopausal (have not experienced a menstrual period in the 12-month period prior to the study).

Safety Population: All VR101 devices in all study arms that are successfully inserted and used in accordance with the provided instructions for use will be included as a basis for determination of SADE proportion.

Claim 1 Population: All participants who report a daily vaginal dryness severity following their first VR101 use (Visit 2/5, depending on study arm) and report a weekly average vaginal dryness severity prior to their first VR101 insertion (Visit 1/4, depending on study arm), will be included in the analysis for Claim 1. See section 5.4.5 for relevant survey questions.

Claim 2 Population: All participants in group V1S2 who respond to the appropriate survey question (see section 5.4.6) immediately following their first VR101 insertion (Visit 1) will be included in the analysis for Claim 2.

Claim 3 Population: All daily diary responses recorded regarding VR101 comfort during use (see section 5.4.6) will be included in the analysis for Claim 3.

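### Claim 1 sets a 24-hour dryness rating on day 7 against a 7-day average before use, with no sham contrast, so it can be validated with no change in user-reported dryness

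*Combined protocol and SAP*

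**What the plan says.** The Claim 1 rule in Section 4.2.3 takes as follow-up the 24-hour "vaginal dryness severity score reported on day 7 (survey question, Visit 2) and average" weekly severity as baseline, the latter being the "vaginal dryness severity score reported over the week prior to VR101 use (survey question, Visit 1 for study group V1S2" and, for the other sequence, "Visit 4 for study group S1V2) is less than 0.05". Section 5.4.5 confirms the pairing by question number: "Responses to Question 2 prior to ring insertion and to Question 4 following use of the first VR101 for 7 days". Endpoint 2 in Section 5.1.1, the Claim 1 population in Section 8.12 and Appendix B all pair the items in the same way, so this is the planned analysis and not a slip in one place.

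Section 8.1 gives the test: "For Primary Efficacy and Validation of Claim 1, the null hypothesis will be rejected based on a two-tailed Student's t-test", with a non-parametric substitute if the data are not normal. Only ratings around the first VR101 period enter, and no direction of change is required. By contrast, the note to Section 4.2.1 requires a positive mean VHI change for the primary endpoint.

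Section 4.2.3 says that at each visit "participants will be asked to rate their vaginal dryness over the last 24 hours and the last 7 days", so a like-for-like pair should exist. No reason is given for crossing the items; Section 6.4 justifies only the use of self-report.

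Sections 4.2.3 and 8.11 test Claim 1 only after the primary efficacy and safety hypotheses are met. Section 8.5 says the claims do not affect trial success.

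**The concern.** A paired difference measures change only if the same quantity is measured twice. Here the difference contains any change in dryness plus the gap between how a woman answers a 7-day-average question and how she answers a 24-hour one.

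The pilot (Section 2.4) suggests that the gap favours the device: "They initially reported experiencing dryness an average of 4 days out of the prior 7 days", yet 20 of 21 women had some dryness in that week. On both items score 0 means no dryness experienced. A woman with any dry day cannot literally choose 0 for the week, but she may truthfully choose it for the last 24 hours. Placebo response and regression to the mean also count as relief, because the matching sham rating is not used.

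Claim 1 is an intended labeling claim and the gate to Claims 2 and 3. Section 6.4 itself says that without user-reported improvement the treatment may not be clinically useful. A test that can pass without such improvement does not serve that purpose.

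**Working it through.** **Plan figures.** The documents give no power, SD or effect size for Claim 1. The nearest figure, 88% power for the primary endpoint (n = 60, difference 0.89, SD 2.14, two-sided 0.05; Section 8.2), reproduces as 88.7% with a noncentral t on 59 df, but it has no bearing on Claim 1.

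**Inputs.** From the documents: 60 completers, a 0–3 scale, two-sided 0.05, and a pilot mean of 4 dry days in 7. Assumed: SD of the paired difference 0.7–1.0; dry-day severity mix of 30% mild, 50% moderate and 20% severe; 6 dry days in 7 as an alternative frequency; and several ways in which women form the weekly rating.

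**Step 1: how small a gap is enough.** The observed mean shift needed is t(0.975, 59) × SD/√60.
- SD 0.7: 2.001 × 0.7/7.746 = 0.18 points.
- SD 1.0: 2.001 × 1.0/7.746 = 0.26 points.

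A true artefactual shift of 0.2 gives p < 0.05 in 33–59% of trials, 0.3 in 63–90%, and 0.5 in 97–100%.

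**Step 2: size of the gap with no change in dryness.** A random untreated day is free of dryness with probability 1 − 4/7 = 3/7 = 43%. Suppose a woman gives her usual dry-day severity s as the weekly rating and is dry on a proportion p of days. The expected difference (24-hour minus weekly) is then s·p − s = −s(1 − p). Mean s is 0.3×1 + 0.5×2 + 0.2×3 = 1.9.
- At 4/7 dry days: −1.9 × 3/7 = −0.81. Simulation gives −0.77, slightly less because a few women have no dry day in the baseline week.
- At 6/7 dry days: −1.9 × 1/7 = −0.27.

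If the weekly rating is instead the rounded mean over all 7 days, the simulated shift at 4/7 is about −0.01.

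**Step 3: null simulation.** Sixty women, the same dryness process before and during use, paired t-test; share of trials with p < 0.05 in the direction of improvement (nominal 2.5%), over 4/7 and 6/7 dry days:

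| How the 7-day rating is formed | False validation |
|---|---|
| True 7-day mean, rounded | 3–7% |
| Same, but at least mild if any day was dry | 9–36% |
| Half of women rate their typical dry day | 28–77% |
| All women rate their typical dry day | 80–100% |
| 24-hour item at both times | 2–3% |

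Wider assumptions about severity mix and day-to-day variability stretch the second row to 5–71%. With 7-day ratings at both times and 4/7 dry days, p < 0.05 in either direction occurred in 0.7–4.9% of trials, at or below the nominal 5%.

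**The case against.** **The gate.** A reader might infer that a device with no effect at all could readily earn Claim 1. The documents do not support this. Claim 1 is reached only after VR101 beats sham on blinded VHI with a positive mean VR101 change, and after safety is met. A device with no effect on VHI passes the efficacy test in its favour about 2.5% of the time. What can be validated falsely is the absence of an effect on what users report. The gate does not cure that, because a clinician-scored VHI difference does not show that women felt relief.

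**The size is assumed.** Women who answer the average question as asked produce almost no inflation, and nothing in the documents shows that they do otherwise. The 4-in-7 frequency is a pilot group mean. The pilot included women with baseline VHI of 23 or more, whom this trial excludes, so trial participants may be dry more often. At 6 of 7 dry days, with the spread between women varied, the half-and-half case falls to 9–40%. This objection stands: a high error rate cannot be asserted. The simulations also cover only the t-test; a signed-rank test would face the same shift but was not simulated.

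**Visit 2.** Read alone, the Section 4.2.3 rule would take a sham-period rating for group S1V2. A reader should not infer that this is planned. Section 8.12 includes those who "report a daily vaginal dryness severity following their first VR101 use (Visit 2/5, depending on study arm"), and Section 5.1.1 and Appendix B agree. It is a wording slip.

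**No sham in the claim.** Claim 1 is worded as relief relative to before use, so a sham contrast is reasonably supportive and not the test itself. A 24-hour rating on day 7 does suit a claim of relief lasting up to 7 days; that justifies the follow-up item, not a different item at baseline.

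**Conclusion.** The point holds as a defect in a gated labeling claim. The items and recall windows differ at the two times, there is no sham term, and no direction is required, so the rule can be met with no change in user-reported dryness. The artefact is either negligible or in the device's favour in every setting tried. False validation runs from about nominal (3–7% against 2.5%) to near 100%, and its place in that range depends on recall behaviour and dryness frequency that the documents do not give. The result of the primary analysis and the success of the trial are unaffected. Using the same item at both times brings the error back to nominal for the recall artefact; placebo response and regression to the mean would remain in any comparison with baseline alone.

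**What to change.** In Sections 4.2.3, 5.1.1, 5.4.5, 8.12 and Appendix B:

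1. Use the 24-hour item at both times: Visit 1 (V1S2) or Visit 4 (S1V2) against Visit 2 (V1S2) or Visit 5 (S1V2).
2. First confirm that the Visit 1 Pre-Study Survey carries that item. Section 4.2.3 and Appendix B say it is asked at each visit, but Section 5.4.5 places it in the Pre-Procedure Survey, which is not used at Visit 1. If it is missing, use the 7-day item at both times.
3. Require the difference to be in the direction of improvement.
4. Change Visit 2 to Visit 2/5 in the Section 4.2.3 rule.
5. As a supportive analysis only, report the within-woman VR101-versus-sham difference in the 24-hour rating at day 7, from data already collected at Visits 2 and 5.

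The cost is wording, provided the Visit 1 form has the item. A one-day baseline is noisier than a weekly one, so some power is lost. The change also comes after 72 women were enrolled (Section 5.3.6), so it should be documented before the crossover blind is broken.

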5 STUDY DESIGN

5.1 General Description of the Clinical Investigation

Clinical Phase: Pivotal

Sample Size: At least 60 participants (up to 69 may be enrolled to account for the anticipated drop-out rate) who consent to be enrolled and meet inclusion/exclusion criteria

Study Population: Women over the age of 35 who self-report having experienced vaginal dryness symptoms that interfere with daily activities, including but not limited to sexual activity, in the last 60 days; and whose clinician-assigned baseline VHI score is 22 or lower.

J3 Bioscience, Inc.	Clinical Investigation Plan and Protocol CI02	CI02-CIP Rev. 08 Page 26 of 75
	A Pivotal Clinical Investigation to Evaluate the Safety and Efficacy of J3 Bioscience Lubricating Intravaginal Ring VR101 in Relieving Symptoms of Vaginal Dryness	

Study Type (Comparative Efficacy): Multi-center, investigator- and participant-blind, randomized crossover study.

Study Type (Long-term Safety): Multi-center, long-term safety evaluation

Study Products: VR101 devices and sham controls (see descriptions above)

Study Regimen: Participants will be randomly assigned to be treated initially by VR101 (GROUP V1S2) or a sham control (GROUP S1V2). Since inclusion in the study will be contingent upon a sufficiently low baseline VHI score, official enrollment and randomization will not occur until the participant's baseline VHI score has been measured and determined to meet the inclusion criterion (Initial VHI \leq 22). Participants randomly assigned to GROUP V1S2 will insert a VR101 ring and leave it in place for 7 days, then remove the first ring and replace it with a fresh ring on day 7. Subsequently, 2 additional rings will be inserted and removed serially on a 7-day schedule until a total of 4 rings are used by each study participant, with the last ring removed at day 28.

Participants assigned to S1V2 will insert a sham control ring and leave it in place for 7 days, then remove the first ring and replace it with a new ring on day 7. Subsequently, 2 additional sham rings will be inserted and removed serially on a 7-day schedule until a total of 4 sham rings are used by each study participant, with the last sham ring removed at day 28.

Following completion of the first 28-day treatment course with either VR101 or sham control, participants will undergo a 21-day “washout” period during which no devices will be used, before “crossing over” to treatment with the other device.

Participants in Group S1V2 will be assigned to complete the long-term safety evaluation. Following the 4-week use of shams and a 3-week washout period, these participants will use a new VR101 device every 7 days for 13 consecutive weeks. V1S2 participants will be transitioned back to VR101 following 4 weeks of sham use, and will use VR101 for 13 additional weeks.

NOTE: VHI scores will be collected during the long-term safety evaluation, but those scores assigned after day 28 will not be used as a measure of device efficacy.

5.1.1 Study Endpoints

Used to Test Primary Efficacy Hypothesis:

1. $\Delta VHI_{VR101}(\text{day 28}) - \Delta VHI_{\text{sham}}(\text{day 28})$, the paired difference in vaginal dryness relief between VR101 and the sham control at day 28.

J3 Bioscience, Inc.	Clinical Investigation Plan and Protocol CI02	CI02-CIP Rev. 08 Page 27 of 75
	A Pivotal Clinical Investigation to Evaluate the Safety and Efficacy of J3 Bioscience Lubricating Intravaginal Ring VR101 in Relieving Symptoms of Vaginal Dryness	

Used for Validation of Claim 1:

2. The paired difference between self-reported 24-hour vaginal dryness severity reported after the first 7 days of VR101 use (see Section 5.4.5, collected at Visit 2 or 5 depending on study group) and weekly-averaged vaginal dryness severity prior to ring use (also see Section 5.4.5, collected at Visit 1 or Visit 4 depending on study group).

Used for Validation of Claim 2:

3. Participant reported ease of use of VR101 (measured on a scale of -4 to 4, see Section 5.4.6).

Used for Validation of Claim 3:

4. Self-reported perception that VR101 was comfortable during use, measured on a scale of -4 to 4 (see Section 5.4.6).

Used to Test Primary Safety Hypothesis:

5. The proportion of Serious Adverse Device Effects (SADE) in relation to the total number of VR101 devices use in the study.

5.1.2 Measures to Minimize Bias

- Clinicians assigned to perform vaginal exams and assign VHI Scores will be blinded from device identity, and thus upon administering an exam will not be aware of whether a patient has inserted a VR101 or a sham ring.
- Because lubricant-filled VR101 devices and unfilled sham rings are very similar in appearance and both are packaged with the same amount of excess glycerol/water solution, it is likely that patients will not know whether they are inserting the test VR101 devices or the sham controls.
- Clinicians assigned to perform vaginal exams and collect VHI Scores will be blinded from accessing any patient data from previous visits pertaining to efficacy endpoints (see section 5.1.1). Thus, on any given visit, the clinician assigned to measure VHI will be unaware of a patient's previous VHI score.
- Participants will not have access to their previous responses, and thus in any given survey where subjective data are collected for the validation of claims, participants will be unable to reference their previous responses.
- Any women who meet inclusion/exclusion criteria and consent to be enrolled in the study will be enrolled and randomly assigned to either the V1S2 or S1V2 treatment group.
- To preserve assigned randomization identity during the crossover study, V1S2 participants will be transitioned back to VR101 following 4 weeks of sham use and will participate in the long-term safety study.

J3 Bioscience, Inc.	Clinical Investigation Plan and Protocol CI02	CI02-CIP Rev. 08 Page 28 of 75
	A Pivotal Clinical Investigation to Evaluate the Safety and Efficacy of J3 Bioscience Lubricating Intravaginal Ring VR101 in Relieving Symptoms of Vaginal Dryness	

5.1.3 Test Equipment, Maintenance, and Calibration

No special test equipment is required for assessing the effects of VR101, with the exception of the assessment of vaginal pH. Vaginal pH shall be measured using Precision Labs Beer pH Strips (Cat. No. PH4662). Operators will be trained use pH strips per the manufacturer's instructions. pH shall be recorded to the nearest 0.2 pH units on the applicable Case Report Form. No other test equipment is needed for evaluation of safety or efficacy of device use.

5.2 Investigational and Predicate Devices

5.2.1 Exposure to VR101 and the sham control

Participants will use VR101 for up to 17 weeks total and the sham control for 4 weeks as described above. Participants will use VR101 for approximately 13 total weeks, consecutively, to evaluate device safety.

